- 309 • PMD with stimulus size V in the best eye qualifying for study entry
- 310 • Papilledema grade (Photographic Reading Center and site investigator ratings)
- 311 • OCT measures of:
 - 312 ♦ Retinal nerve fiber layer thickness
 - 313 ♦ Retinal ganglion cell layer thickness
 - 314 ♦ Peripapillary retinal pigment epithelial (RPE)/Bruch's membrane deformation
- 315 • CSF pressure
- 316 • Visual acuity
- 317 • Quality of life (QoL) measures (NEI-VFQ-25 + 10-item neuro-ophthalmic supplement
 318 and the SF-36)
- 319 • Headache disability (HIT-6 Inventory)
- 320 • Headache severity

321 Other efficacy outcome variables, determined at Month 6, include treatment failure, surgical
 322 failure, presence of headache, presence of transient visual obscurations, and visual field
 323 examination ratings (improved, no change, worse) by the Visual Field Reading Center.

324 With the exception of CSF pressure, these outcome variables will also be examined at Months
 325 12, 24 and 36.

326 Of special interest and a very important outcome is the time from randomization to treatment
 327 failure. Subjects will be followed for up to 3 years and the number of surgical failures and
 328 treatment failures will be analyzed. While a therapy may have a beneficial outcome at 6 months,
 329 it may not have a good outcome 1-3 years later; therefore, this is an important analysis.

330 Measures of safety include the following:

- 331 • Adverse events
- 332 • Serious adverse events
- 333 • Procedure complications and transient malfunctions of surgical procedures
- 334 • Blood pressure
- 335 • Laboratory test results (CBC with platelet count, electrolytes, potassium, bicarbonate, and
- 336 liver function tests)

337 **1.4.3 Other Outcomes**

- 338 • Anthropometric measures (weight, waist circumference)

339 **1.5 Potential Risks and Benefits of the Study Interventions**

340 **1.5.1 Known Potential Risks**

341 **1.5.1.1 Visual Loss**

342 The primary risk of IIH is visual loss associated with papilledema. Subjects reaching treatment
343 failure criteria will remain in the study but will be managed by the site investigators.

344 **1.5.1.2 Acetazolamide**

345 Acetazolamide frequently causes paresthesias, altered taste sensation, asymptomatic metabolic
346 acidosis (low serum bicarbonate), and fatigue. There is a small risk of kidney stones, and, very
347 rarely, renal failure from acute tubular necrosis, liver enzyme changes, elevation of serum

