7.1.1 Definitions

1173 Adverse Event (AE): Any untoward medical occurrence in a study subject, irrespective of the
1174 relationship between the adverse event and the study drug or surgery (see 7.1.2 for what adverse
1175 events require reporting in this protocol).

1176 Serious Adverse Event (SAE): Any untoward medical occurrence that:

- 1177 • Results in death.
- 1178 • Is life-threatening; (a non-life-threatening event which, had it been more severe, might
1179 have become life-threatening, is not necessarily considered a serious adverse event).
- 1180 • Requires inpatient hospitalization or prolongation of existing hospitalization.
- 1181 • Results in persistent or significant disability/incapacity or substantial disruption of the
1182 ability to conduct normal life functions.
- 1183 • Is a congenital anomaly or birth defect.
- 1184 • Is considered a significant medical event by the investigator based on medical judgment
1185 (e.g., may jeopardize the subject or may require medical/surgical intervention to prevent
1186 one of the outcomes listed above).

1187

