7.1.2 Reporting Adverse Events

1188 Symptoms and signs, including visual symptoms and headaches, that are considered to be due to
1189 IIIH will be captured on a visit/phone case report form and are not considered to be adverse
1190 events unless SAE criteria are met.

1191 Certain adverse events that are known side effects of acetazolamide and furosemide will be
1192 captured on a visit/phone case report form (including paresthesia, dizziness, nausea, vomiting,
1193 diarrhea, loss of appetite, acid reflux, skin rash, dyspnea, hypercapnia, depression, anxiety,
1194 tinnitus, fatigue) for all subjects, regardless of whether taking study medication. A separate
1195 Adverse Event Form is only completed for these specific events if SAE criteria are met or the
1196 event was severe enough that it resulted in discontinuation of study drug.

1197 Expected symptoms post-surgery will be captured on a visit/phone case report form. A separate
1198 Adverse Event Form is only completed for these specific events if SAE criteria are met or if the
1199 onset date is outside the expected duration of occurrence post-surgery, regardless of intensity.

1200 Laboratory results of interest will be recorded on a laboratory data case report form. A separate
1201 Adverse Event Form is only completed for laboratory abnormalities that are considered clinically
1202 significant by the investigator.

1203 During the first 6 months, all other events (not described above) meeting the definition of
1204 adverse event will be reported on an Adverse Event Form. After the first 6 months, only those
1205 events meeting SAE criteria will be reported on an Adverse Event Form.

1206 **7.1.3 Relationship of Adverse Event to Study**

1207 The study investigator will assess the relationship of any adverse event reported on an Adverse
1208 Event Form to be related or unrelated to a study intervention or procedure by determining if there
1209 is a reasonable possibility that the adverse event may have been caused by the intervention or
1210 procedure.

1211 To ensure consistency of adverse event causality assessments, investigators should apply the
1212 following general guideline when determining whether an adverse event is related:

1213 Yes

1214 There is a plausible temporal relationship between the onset of the adverse event and the study
1215 intervention/procedure, and the adverse event cannot be readily explained by the subject's

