1216 clinical state, intercurrent illness, or concomitant therapies; and/or the adverse event follows a
1217 known pattern of response to the study intervention/procedure; and/or the adverse event abates or
1218 resolves upon discontinuation of the study intervention/procedure or dose reduction and, if
1219 applicable, reappears upon re-challenge.

1220 No

1221 Evidence exists that the adverse event has an etiology other than the study
1222 intervention/procedure (e.g., preexisting medical condition, underlying disease, intercurrent
1223 illness, or concomitant medication); and/or the adverse event has no plausible temporal
1224 relationship to study intervention/procedure.

1225 **7.1.4 Intensity of Adverse Events**

1226 The intensity of an adverse event will be rated on a three-point scale: (1) mild, (2) moderate, or
1227 (3) severe. It is emphasized that the term severe is a measure of intensity; thus, a severe adverse
1228 event is not necessarily serious. For example, itching for several days may be rated as severe,
1229 but may not be clinically serious.

- 1230 • MILD: Usually transient, requires no special treatment, and does not interfere with the
1231 subject's daily activities.
- 1232 • MODERATE: Usually causes a low level of inconvenience or concern to the subject and
1233 may interfere with daily activities, but is usually ameliorated by simple therapeutic
1234 measures.
- 1235 • SEVERE: Interrupts a subject's usual daily activities and generally requires systemic
1236 drug therapy or other treatment.

1237 **7.1.5 Coding of Adverse Events**

1238 Adverse events will be coded using the MedDRA dictionary.

1239 **7.1.6 Outcome of Adverse Event**

1240 The outcome of each reportable adverse event will be classified by the investigator as follows:

- 1241 • RECOVERED/RESOLVED: The subject recovered from the AE/SAE without sequelae.
1242 Record the AE/SAE stop date.
- 1243 • RECOVERED/RESOLVED WITH SEQUELAE: The event persisted and had stabilized
1244 without change in the event anticipated. Record the AE/SAE stop date.
- 1245 • NOT RECOVERED/NOT RESOLVED: An ongoing AE/SAE is defined as the event
1246 was ongoing with an undetermined outcome.
- 1247 ◆ An ongoing outcome will require follow-up by the site in order to determine the final
1248 outcome of the AE/SAE.
- 1249 ◆ The outcome of an ongoing event at the time of death that was not the cause of death,

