1281 abiding by any other reporting requirements specific to his/her Institutional Review Board or
1282 Ethics Committee.

1283 The sponsor will report any serious, unexpected treatment-related adverse events to the FDA.

1284

1285 **7.4 Stopping Criteria**

1286 **7.4.1 Subject Discontinuation of Study Drug**

1287 Rules for discontinuing study drug use are described below.

- 1288 • The investigator believes it is unsafe for the subject to continue to receive the drug. This
1289 could be due to the development of a potential side effect of the drug, a new medical
1290 condition or worsening of an existing condition; or subject behavior contrary to the
1291 indications for use of the drug that imposes on the subject's safety
- 1292 • The subject requests that the treatment be stopped
- 1293 • Subject pregnancy during 6-month RCT (discontinuation at investigator discretion during
1294 Treatment Failure Identification Phase)

1295 Even if the study drug is discontinued, the subject will be encouraged to remain in the study
1296 through the final study visit.

1297 **7.5 Medical Monitor**

1298 A Medical Monitor will review all reported adverse events reported on an Adverse Event Form,
1299 solicited events captured on a visit/phone case report form, and laboratory abnormalities.

1300 The Medical Monitor will assess each event for appropriate coding of intensity, criteria for SAE,
1301 relationship to study drug/procedure, and MedDRA classification. The Medical Monitor's
1302 coding will be considered final.

1303 **7.6 Independent Safety Oversight**

1304 A Data and Safety Monitoring Committee (DSMC), selected by the National Eye Institute, will
1305 provide study oversight. The Committee will be sent serious, unexpected, treatment-related
1306 adverse events for expedited review and all adverse events in a cumulative report approximately
1307 every 6 months.

1308 **7.7 Criteria for Suspending or Terminating Overall Study**

1309 There are no pre-specified criteria for suspending or terminating the study. Such decisions will
1310 be made by the DSMC based on their review of accumulated safety data.

1311

Chapter 8: Miscellaneous Considerations

1312

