1537 Schoenfeld residuals¹⁰¹. This assumption will also be examined by dividing the time scale into 6-
1538 month periods and estimating the treatment group hazard ratios separately in each of these
1539 periods through the use of time-dependent covariates¹⁰³. The period length of 6 months may be
1540 adjusted prior to unmasking, based on the observed distribution of event times, if relatively few
1541 events occur during 6-month periods. Treatment group comparisons will be described in this
1542 manner if the proportional hazards assumption appears to be seriously violated.

1543 An additional important assumption of the methods to be used to analyze time to treatment
1544 failure is the independence between the censoring time and the (unobserved) event time.
1545 Sensitivity analyses will be performed that treat subjects with event times that are censored prior
1546 to their scheduled end of follow-up as having experienced the event a short time (one week) after
1547 censoring.

1548 Analyses of the primary and secondary outcome variables for efficacy using data collected after
1549 the 6-month visit will be analyzed according to the initial treatment strategy using the same
1550 methods described above. This will include surgical procedure complications or transient
1551 malfunctions. More complex analyses may be performed that take into account the introduction
1552 of other treatments (e.g., surgery in those assigned to medical therapy) depending on how often
1553 this occurs. It will necessarily be difficult to make inferences about the effectiveness of
1554 subsequent treatments; however, analyses using marginal structural models^{100,104} may prove
1555 useful for this purpose. Outcomes such as surgical failure and IIH recurrence (in those whose
1556 vision is initially restored) will be summarized descriptively over time.

1557 **9.8 Interim Analyses**

1558 **9.8.1 Interim Analyses for Safety**

1559 Interim analyses of safety data will be performed periodically throughout the trial. While the
1560 safety of subjects will be the primary concern of the DSMC, it is difficult to formulate precise
1561 stopping guidelines that would cover all of the possible situations that might arise. Adverse
1562 events, particularly serious adverse events and surgical complications, will have to be considered
1563 carefully by the DSMC in terms of treatment group imbalances and severity. Events of particular

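### After Month 6 an unexpected, non-serious complication of IIH surgery has no Adverse Event Form, and SAP 3.8 lists surgical complications for the six-month trial only

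*Protocol*

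**What the plan says.** Protocol 7.1.2 first gives separate routes to IIH symptoms, listed acetazolamide and furosemide side effects, expected post-surgical symptoms and laboratory results. For everything else it draws a line at six months: "adverse event will be reported on an Adverse Event Form. After the first 6 months, only those" that meet SAE criteria go on the form.

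Two later steps depend on the form. On relatedness, 7.1.3 says: "The study investigator will assess the relationship of any adverse event reported on an Adverse" Event Form. On central review, 7.5 says: "A Medical Monitor will review all reported adverse events reported on an Adverse Event Form", and adds solicited visit or phone events and laboratory abnormalities.

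Complications of surgery are a stated interest. Section 1.4.2 lists among the safety measures "Procedure complications and transient malfunctions of surgical procedures". Section 9.7, on data collected after the six-month visit, refers to the "methods described above. This will include surgical procedure complications or transient" malfunctions. Section 9.8.1 tells the DSMC that adverse "events, particularly serious adverse events and surgical complications, will have to be considered" carefully.

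SAP 3.8 has a general list, a list for the 6-Month RCT and a list for the later phase. Surgical complications, ONSF reoperations and shunt revisions appear only in the 6-Month RCT list.

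**The concern.** The reporting period is counted from randomization, but the risk of a surgical complication runs from the operation. The protocol expects some operations after Month 6:

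- ONSF of a non-eligible eye that worsens, at any point in follow-up (4.2, 4.6);
- reoperation after a malfunction, with no time limit (5.1.2, 5.6.2);
- treatment from another arm after treatment failure, which can mean a first VPS or ONSF (4.7, 5.7.2).

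The same unexpected, non-serious complication is therefore put on a form and assessed for relatedness if it occurs in Month 3, but not if it follows an operation in Month 14. Non-serious does not mean mild: 7.1.4 says that a severe event need not be serious, and describes severe events as interrupting usual activities and generally needing treatment. At stake is whether the long-term account of surgical complications, which 9.7 promises and 9.8.1 asks the DSMC to weigh, includes these events.

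**Working it through.** The plan gives no figure to reproduce. The check is to follow one event through the text and then to count the SAP lists.

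**One event.** Take an unexpected complication of an operation in Month 14. It needs treatment without admission, and the investigator does not judge it medically significant.

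1. Own route in 7.1.2? It is not an IIH symptom, a listed drug effect, an expected post-surgical symptom or a laboratory result, so the residual rule applies.
2. Form under the residual rule? After Month 6 only if serious. It is not serious, so no Adverse Event Form. No clause refers to the date of an operation.
3. Malfunction review under 5.6? Only if a malfunction is suspected. By assumption it is not.
4. Relatedness under 7.1.3? Required only for events on the form, so not required.
5. Medical Monitor under 7.5? It is not on a form, not a solicited visit or phone event and not a laboratory abnormality, so no route is described.
6. Coding? Section 7.1.5 says "Adverse events will be coded using the MedDRA dictionary" without restricting this to forms, so the position is unclear.
7. DSMC under 7.6? The committee receives a cumulative report of all adverse events about every six months. That wording is not limited to forms. But the adverse event definition in 7.1.1 points to 7.1.2 for what must be reported, so 7.6 does not clearly bring the event in.
8. SAP 3.5.1? It tabulates reportable events, and on the reading above this is not one.

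**An inconsistency inside 7.1.2.** An expected post-surgical symptom that starts outside its expected period needs a form whatever its intensity, and that paragraph states no six-month limit. If it continues after Month 6, a mild expected symptom of late onset gets a form while a severe unexpected complication does not. If the final sentence of 7.1.2 overrides it, more events lose their form.

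**SAP 3.8 by count.**

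| List | Items | Surgical items |
|---|---|---|
| General | 7 | 2: overall malfunctions; days from randomization to surgery |
| 6-Month RCT | 16 | 6: surgery other than assigned, ONSF completion, VPS completion, complications, reoperations, shunt revisions |
| Later phase | 4 | 0: adherence, dosage, medical therapy, protocol deviations only |

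Complications, reoperations and shunt revisions are 3 of 3 in the 6-Month RCT list and 0 of 3 in each of the others. SAP 3.6 names only time to treatment failure as a long-term outcome.

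**The case against.** SAE-only reporting in an extension phase is an ordinary design choice, and most late complications that matter would still be reported. The SAE definition covers hospitalization, and its last criterion reads "Is considered a significant medical event by the investigator based on medical judgment". Most of the events that 9.8.1 names, such as orbital infection, seizures and subdural hematoma, would meet SAE criteria or follow the malfunction, treatment-failure or laboratory route. Adverse events are asked about at the 39-week call and at every later and unscheduled visit (1.8.2), and the later history update records new treatments (5.2.2). The case report forms and MOP, which would show what is written down, are not in the documents. On the analysis side, SAP 3.8 is a list of additional tabulations and does not claim to be complete. Late serious complications appear under SAP 3.5.1, and malfunctions are counted overall.

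All of this stands, and it makes the class small. It does not close the gap. Asking about an event does not make it reportable when 7.1.1 refers to 7.1.2 for that decision. None of these routes describes a relatedness assessment or Medical Monitor review for the event traced above. The SAP omission does not depend on what the unseen forms collect.

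A reader might go further and infer that late surgical complications in general go unreported, or that the DSMC cannot see them. The documents do not support that: serious events, malfunctions and expected symptoms keep their routes, and 7.6 is worded broadly. Nor do they support a claim of bias towards one arm, because the rule applies to all arms. Nor can the 40% shunt-failure figure in protocol Table 3 be used to size the gap, because failures are not the non-serious complications at issue and malfunctions have their own review.

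**Conclusion.** The point holds in a limited form. As written, 7.1.2 leaves unexpected, non-serious, non-malfunction complications of surgery after Month 6 without an Adverse Event Form, a required relatedness assessment or a described route to the Medical Monitor. SAP 3.8 omits from its later-phase list the complications that protocol 9.7 says will be analysed, together with reoperations and shunt revisions.

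The number of affected events cannot be estimated. The documents give no non-serious complication rate, no expected number of late operations and no list of expected post-surgical symptoms. The only countable result is the SAP gap: 3 surgical rows in the 6-Month RCT list and none of the 3 in the later-phase list.

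The conclusion about reporting assumes that 7.1.2 governs what is reported, as 7.1.1 indicates, and that no surgical case report form or MOP instruction already collects these events after Month 6. If one does, the protocol needs only to say so and to send the events for review. This is a cheap improvement and does not threaten the primary result.

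**What to change.** 1. **Protocol 7.1.2.** After Month 6, report on an Adverse Event Form any adverse event with onset within a fixed window (for example 30 days) after any IIH operation, or judged possibly related to one, and link it to that operation. Cover VPS, ONSF, revision, reoperation, fellow-eye and rescue surgery. Keep SAE-only reporting otherwise. Counting from the operation also covers one done shortly before Month 6. If a surgical case report form already collects these events, say so and send them for relatedness assessment and Medical Monitor review.
2. **SAP 3.8.** Add surgical complications, reoperations and shunt revisions to the later-phase list. Tabulate complications per operation over the same window for the whole of follow-up, and list related events outside the window separately.

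The cost is a minor amendment with IRB approval (11.2), one link field, a few extra forms and one table. Post-operative safety visits are clearly provided for reoperations at any time (5.1.2). The wider statement in the 1.8.1 footnote, that safety visits are repeated after each procedure, belongs to the six-month schedule. For a first rescue operation after treatment failure, collection would rely on unscheduled visits, the surgeon's routine post-operative visits or the next contact. The 30-day figure is a suggestion; the need is for a stated window tied to the operation.

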1250 will be updated and recorded as “resolved” with the date of death recorded as the stop
1251 date.
- 1252 • FATAL: A fatal outcome is defined as the SAE that resulted in death. Only the event
1253 that was the cause of death should be reported as fatal. AEs/SAEs that were ongoing at
1254 the time of death; however, were not the cause of death, will be recorded as “resolved” at
1255 the time of death.
- 1256 • UNKNOWN: An unknown outcome is defined as an inability to access the subject or the
1257 subject’s records to determine the outcome (for example, a subject that was lost to
1258 follow-up).

1259 All clinically significant abnormalities of clinical laboratory measurements or adverse events
1260 occurring during the study and continuing at study termination should be followed by the
1261 subject’s physician and evaluated with additional tests (if necessary) until diagnosis of the
1262 underlying cause, or resolution. Follow-up information should be recorded on source
1263 documents.

1264 If any reported adverse events are present when a subject completes the study, or if a subject is
1265 withdrawn from the study due to an adverse event, the subject will be contacted for re-evaluation
1266 within 2 weeks. If the adverse event has not resolved, additional follow-up will be performed as
1267 appropriate. Every effort should be made by the Investigator or delegate to contact the subject
1268 until the adverse event has resolved or stabilized.

1269 **7.2 Pregnancy Reporting**

1270 If pregnancy occurs during the 6-month RCT, study drug will be discontinued. The occurrence of
1271 pregnancy will be reported on an AE Form.

1272 **7.3 Timing of Event Reporting**

1273 Serious, unexpected treatment-related adverse events must be reported to the Coordinating
1274 Center within 24 hours via completion of the online serious adverse event form.

1275 Other reportable adverse events as defined in section 7.1.2 will be reported within 3 days of the
1276 investigator becoming aware of the event by completion of an electronic case report form.

1277 The Coordinating Center will notify all participating investigators of any adverse event that is
1278 serious, related, and unexpected. Notification will be made within 10 working days after the
1279 Coordinating Center becomes aware of the event.

1280 Each principal investigator is responsible for reporting serious study-related adverse events and

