1564 concern include the following: death, absence of light perception, hypokalemia (from Lasix use),
1565 surgery-associated visual loss (from either VPS or ONSF), fenestration failure and orbital
1566 infection (from ONSF), and shunt failure, infection, seizures, and subdural hematoma (from
1567 VPS). If potential safety concerns are identified, the DSMC may require review of visual field
1568 data in order to evaluate the risk-benefit of continuing the trial as planned or modifying (or
1569 halting) the trial.

1570 **9.8.2 Interim Analyses for Efficacy**

1571 We propose to perform a single interim analysis for efficacy based on the primary outcome
 1572 efficacy variable. This will be performed after 50% of the subjects have completed (or were
 1573 scheduled to have completed, based on their randomization date) their Month 6 visit and will
 1574 only include data from these 50% of subjects. Given that recruitment of the 180 subjects will
 1575 take place over 3 years, assuming that recruitment is uniform over time, it is anticipated that
 1576 slightly fewer than 70% of the subjects will be enrolled at the time of the interim analysis.

1577 The analysis will involve pair-wise comparisons among the treatment groups with respect to the
 1578 primary outcome efficacy variable; the significance level used for each comparison will be that
 1579 determined by an O'Brien-Fleming α -spending function for a two-group comparison divided by
 1580 3 (Bonferroni correction).⁹⁹ In this case, the boundaries will be $Z = 3.394$ for the interim analysis
 1581 and $Z = 2.400$ for the final analysis. Assuming that there are 30 subjects per group and that the
 1582 standard deviation is 6.5 dB at the interim analysis, the boundary will be crossed if a group
 1583 difference exceeds approximately 5.7 dB. This monitoring procedure will have a negligible
 1584 impact on the overall Type I error probability: the significance level at the final analysis
 1585 corresponding to $Z = 2.400$ is $\alpha = 0.0164$. Point and interval estimates of treatment effects, as
 1586 well as reported p-values, will be adjusted for the interim analysis. The bias-adjusted mean will
 1587 be used for point estimation and confidence intervals and p-values based on the MLE (sample
 1588 mean) ordering of the sample space defined by the group sequential design^{97,98} will be reported
 1589 in this case.

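### Deaths judged unrelated, and serious surgical complications classed as expected, have no expedited route to the DSMC and can wait for a report issued about every 6 months

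*Protocol*

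**What the plan says.** Protocol section 7.6 gives the DSMC two routes of information. For the first, "The Committee will be sent serious, unexpected, treatment-related" events go for expedited review. The second is the cumulative report: "adverse events for expedited review and all adverse events in a cumulative report approximately" every 6 months. Section 7.3 applies the same three-part filter to 24-hour reporting by sites: "Serious, unexpected treatment-related adverse events must be reported to the Coordinating" Center on that timescale. Other reportable events are due within 3 days.

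Protocol section 9.8.1, repeated in SAP section 3.7.1, tells the DSMC what to watch. Events of particular "concern include the following: death, absence of light perception, hypokalemia (from Lasix use"), then "surgery-associated visual loss (from either VPS or ONSF), fenestration failure and orbital" "infection (from ONSF), and shunt failure, infection, seizures, and subdural hematoma (from" VPS). On timing, both sections say only: "Interim analyses of safety data will be performed periodically throughout the trial. While the" safety of subjects is the DSMC's foremost priority. Neither gives an interval shorter than that of section 7.6.

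On stopping, section 7.7 states: "There are no pre-specified criteria for suspending or terminating the study. Such decisions will" rest with the DSMC, on its review of accumulated safety data.

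**The concern.** The expedited rule and the watch list do not meet. The list contains events chosen because they are foreseeable consequences of the two operations, or because they are grave whatever their cause. The rule expedites an event only if it was not foreseen and is attributed to treatment. An event can therefore be on the list and still fail the rule, either because it was foreseen or because it was judged unrelated.

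This matters more here than in many trials. Two of the three arms are surgical, surgery follows within 7 days of randomization, and there is no numerical safety boundary. Without one, the time at which the DSMC sees the data determines how soon it can act on a cluster of complications while randomization to the same procedure continues.

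**Working it through.** This is mainly a reading of the text, with a short calculation for scale.

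**1. Which events fail the filter?** Three conditions must all hold.

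- *A death judged unrelated* fails the treatment-related condition by definition. No inference is needed.
- *A serious, related complication that is classed as expected* fails the unexpected condition. Whether a given complication is so classed cannot be settled from these documents. Neither defines the term. Section 7.1.2 mentions expected symptoms after surgery without listing them. Section 1.5.1 (known risks) covers visual loss, acetazolamide and furosemide, but no surgical risks. The Medical Monitor's tasks in section 7.5 cover intensity, seriousness, relatedness and coding, not expectedness.
- The background text supports calling some events expected: Table 3 totals 40% shunt failures, and Table 2 gives 13% with worse vision after ONSF. Section 7.1.3 counts a known pattern of response as evidence of relatedness, and the same known pattern is a natural reason to call an event expected.

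**2. Is there another timed route to the DSMC?** The other candidate steps are these.

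| Step | Section | Written as a timed notice to the DSMC? |
|---|---|---|
| Other reportable events to the Coordinating Center in 3 days | 7.3 | No |
| Medical Monitor reviews reported events | 7.5 | No |
| Investigator reports serious study-related events as the site's IRB requires | 7.3 | No |
| SMRC reviews suspected malfunction | 5.6, 10.5.6 | No |
| Adjudication Committee decisions sent to the DSMC | 10.5.7 | Sent, but no timing, and only for possible treatment failure |
| Periodic safety analyses | 9.8.1, SAP 3.7.1 | No interval given |

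**3. How many subjects are exposed between two reports?** Inputs: 180 subjects, uniform accrual over 3 years (9.8.2), allocation 1:1:1 (3.2).

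Check of the accrual model against the plan's own figure: half the subjects are enrolled at month 18 and reach Month 6 at month 24, so (18 + 6)/36 = 66.7% are enrolled at the interim analysis. The plan says slightly fewer than 70%, which agrees.

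Per 6 months: 180/36 × 6 = 30 subjects; 30/3 = 10 per arm.

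**4. How likely are events among those 10?** The documents give no rates for most individual complications, so the risk p is an assumption, shown over a range. Binomial, n = 10:

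P(at least 1) = 1 − (1 − p)^10

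P(at least 2) = 1 − (1 − p)^10 − 10p(1 − p)^9

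| Assumed p | At least 1 | At least 2 |
|---|---|---|
| 1% | 10% | 0.4% |
| 5% | 40% | 9% |
| 10% | 65% | 26% |
| 20% | 89% | 62% |

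The count of 10 is simplified in both directions. It leaves out subjects operated on earlier who remain at risk, and it treats every complication as falling in the interval in which the subject was randomized.

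**5. Would expediting every listed event be a light burden?** Table 3 failures sum to 196/490 = 40.0%, the stated total; the rows with VP shunts only give 37/101 = 36.6%. Applied to 60 VPS subjects, 40% is 24 failures. A revision that needs hospital admission meets the serious-event definition in 7.1.1. This is an upper illustration, since the case series had longer and varied follow-up, but it shows that expediting all shunt failures could mean many reports.

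**The case against.** The best defence has four parts.

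*The filter is deliberate and consistent.* The same serious, unexpected and related test governs reports to the FDA and notices to investigators, and section 9.8.1 explains why precise stopping guidelines were not set. This stands: the plan does not contradict itself.

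*Expectedness is not settled.* A reader might infer that none of the listed complications would ever be expedited. The documents do not support that. If expectedness were judged against section 1.5.1, which names no surgical risk, serious seizures, subdural hematomas or orbital infections could count as unexpected and be expedited. The manual of procedures may also say more, but it is not among these documents. What stands is that the route depends on an undefined word.

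*Others see the events sooner.* A reader might infer that nobody learns of these complications for months. That is wrong: the Coordinating Center has them within 3 days, the Medical Monitor reviews them, and suspected malfunction can go to the SMRC. A surgical quality committee also provides quality control. These steps protect individual subjects, but none is written as a trigger for timely notice to the DSMC.

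*A run of events within one interval need not be likely.* Three or more events among 10 has probability 32% at a 20% risk, but 7% at 10% and about 1% at 5%. The 20% figure is an upper-end assumption and should not be quoted alone.

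**Conclusion.** The concern holds in a limited form. Under the rule as written, a death judged unrelated is not expedited to the DSMC. A serious surgical complication is not expedited either, if it is classed as expected. Both can wait up to about 6 months for the body that decides on suspension, in a trial with no pre-specified stopping criteria. The part on unrelated deaths follows directly from the text. The part on complications rests on how expectedness is assigned, which is likely for well-described risks such as shunt failure and open for the others.

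On size, about 10 subjects per surgical arm enter between reports. The chance of at least one event of a given kind among them runs from 10% to 89% as the assumed risk goes from 1% to 20%.

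This is a gap between a reporting rule and a watch list, worth closing because it is cheap. It is not a flaw in the analysis, nor evidence that safety is unmonitored between reports.

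**What to change.** In Protocol 7.3 and 7.6, with cross-references in 9.8.1 and SAP 3.7.1, state that the following go to the Coordinating Center within 24 hours and to the DSMC for expedited review, whatever their expectedness or judged relatedness:

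- any death;
- any serious case of loss of light perception, visual loss associated with surgery, orbital infection, shunt infection, seizure or subdural hematoma.

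Define unexpected for ONSF and VPS, for example by a reference list of anticipated complications, and name the role that decides it.

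Keep shunt failure, fenestration failure and hypokalemia in the cumulative report unless the DSMC asks otherwise. Expediting every shunt failure would be a real trade-off, given the 40% total in Table 3.

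The cost is a few sentences, one definition and a small number of extra expedited reports. Treatment, visits and the efficacy analysis do not change.
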